Clinical laboratory test values are potentially clinically important (PCI) if they meet either the low or high PCI criteria listed in [Table 2](#). The number and percentage of subjects with post-baseline PCI values will be tabulated. The percentages will be calculated relative to the number of subjects with at least 1 available post-baseline assessment per parameter. The numerator is the total number of subjects with at least 1 post-baseline PCI value. A supportive listing of subjects with post-baseline PCI values will be provided including the subject number, site, baseline, and post-baseline values.

Table 2: Criteria for Potentially Clinically Important Laboratory Tests

| Parameter | SI Unit | Lower Limit | Higher Limit |
|------------------------------|---------|-------------|-------------------------|
| Biochemistry | | | |
| Albumin | g/dL | <3g/dL | - |
| Aspartate transaminase (AST) | - | - | ≥3 x ULN |
| Alanine transaminase (ALT) | - | - | ≥3 x ULN |
| Blood urea nitrogen | mg/dl | - | >30 mg/dl or >2.5 x ULN |
| Calcium | mg/dL | <8mg/dL | >11.5mg/dL |
| Total cholesterol | mg/dL | - | >300mg/dl |
| Creatinine | mg/dl | - | >2 mg/dl or >1.5 x ULN |
| Gamma glutamyl transferase | - | - | ≥2.5 x ULN |
| Glucose | mg/dL | <55mg/dL | >160mg/dL |
| Lactate dehydrogenase | - | - | >3 x ULN |
| Phosphorus | mg/dL | <2.5mg/dL | >7mg/dL |

Table 2: Criteria for Potentially Clinically Important Laboratory Tests

| Parameter | SI Unit | Lower Limit | Higher Limit |
|-----------------------------|---------------------|--------------------------------|----------------------------------|
| Potassium | mmol/l | <3mmol/l | >5.5mmol/l |
| Thyroid stimulating hormone | - | <LLN | >2 x ULN |
| Sodium | mEq/L | <130mEq/L | >150mEq/L |
| Uric acid | mg/dL | - | >10mg/dL |
| Total bilirubin | mg/dL | - | >2 mg/dL |
| Total protein | g/dL | <5g/dL | >9g/dL |
| Hematology | | | |
| Bands | - | - | >0.27x10 ³ /µL or >5% |
| Basophils | - | - | >10% |
| Hemoglobin | g/dL | <9g/dL | >16g/dL |
| Hematocrit | % | <30% | >50% |
| Platelet count | 10 ³ /µL | <75x10 ³ /µL | >600x10 ³ /µL |
| Red blood cells | 10 ⁶ /µL | <2.5x10 ⁶ /µL | - |
| White blood cell count | 10 ³ /µL | <3x10 ³ /µL | >16x10 ³ /µL |
| Neutrophils | - | <1x10 ³ /µL or <30% | - |
| Eosinophils | % | - | >10% |
| Lymphocytes | % | <10% | >70% |
| Monocytes | % | - | >20% |
| Urinalysis | | | |
| Glucose | - | - | Positive Value (excluding trace) |
| Protein | - | - | Positive Value (excluding trace) |

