All vital sign values, include an unscheduled visit, will be considered PCI if they meet either the observed value criteria or the change from baseline criteria listed in [Table 3](#). The number and percentage of subjects with PCI post-baseline values will be tabulated by treatment group. The percentages for the observed value criteria will be calculated relative to the number of subjects with at least 1 post-baseline assessment available per parameter and visit. The percentages for the change from baseline criteria will be calculated relative to the number of subjects with available baseline and at least 1 post-baseline assessment per parameter and visit. The numerator is the total number of subjects with at least 1 PCI post-baseline vital sign value. A supportive listing of subjects with post-baseline PCI values will be provided including the subject number, site, baseline, and post-baseline PCI values.

Table 3: Criteria for Potentially Clinically Significant Vital Signs

| Vital Sign Parameter | Flag | Criteria ^a | |
|---|------|-----------------------|----------------------|
| | | Observed Value | Change from Baseline |
| Sitting systolic blood pressure (mmHg) | High | ≥120 | Increase of >10 |
| | Low | <75 | Decrease of >10 |
| Sitting diastolic blood pressure (mmHg) | High | ≥85 | Increase of >10 |
| | Low | <40 | Decrease of >10 |
| Pulse rate (beats per minute) | High | ≥130 | Increase of >15 |
| | Low | ≤55 | Decrease of >15 |
| Weight (kg) | High | - | Increase of ≥7% |
| | Low | - | Decrease of ≥7% |

Table 3: Criteria for Potentially Clinically Significant Vital Signs

| Vital Sign Parameter | Flag | Criteria ^a | |
|--------------------------|------|----------------------------------|----------------------|
| | | Observed Value | Change from Baseline |
| Temperature (deg. C) | High | >39 | - |
| | Low | <35 | - |
| BMI (kg/m ²) | High | >95th percentile for age and sex | - |
| | Low | <5th percentile for age and sex | - |

BMI=body mass index

^a A post-baseline value is considered as a PCI value if its meets either the criteria for observed value or the criteria for change from baseline.

11.4 **Electrocardiogram (ECG)**

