Descriptive statistics (n, mean, SD, minimum, median, and maximum) for ECG variables (heart rate, PR interval, RR interval, QRS interval, QT interval, and QTc interval) and their changes from baseline at each assessment time point will be presented by treatment group. QTc interval will be calculated using both Bazett ($QTcB = QT/(RR)^{1/2}$) and Fridericia ($QTcF = QT/(RR)^{1/3}$) corrections; if RR is not available, it will be replaced with 60/hr in the correction formula. ECG interpretation will be summarized by visit (and Visit 6/ET) and treatment group. A shift table from baseline to each visit (and Visit 6/ET) for qualitative ECG results will also be presented.

All ECG values will be listed for the Safety Analysis Set.

Electrocardiogram variable values, include unscheduled visit, will be considered PCI if they meet either the observed value criteria or the change from baseline criteria listed in [Table 4](#). The number and percentage of subjects with post-baseline PCI values will be tabulated by treatment group. The percentages for the observed value criteria will be calculated relative to the number of subjects with at least 1 post-baseline assessment available per parameter and visit. The percentages for the change from baseline criteria will be calculated relative to the number of subjects with available baseline and at least 1 post-baseline assessment per parameter and visit. The numerator is the total number of subjects with at least 1 PCI post-baseline ECG value. A listing of all subjects with post-baseline PCI value will be provided including the subject number, site, baseline, and post-baseline PCI values.

Table 4: Criteria for Potentially Clinically Important ECG Values

| ECG Parameter | Unit | Observed Value | | Change from Baseline | |
|---------------|--------------|----------------|--|----------------------|--------------|
| | | Lower Limit | Higher Limit | Lower Limit | Higher Limit |
| ECG Result | - | - | Abnormal (core lab) and clinically significant from investigator | - | - |
| Heart Rate | Beats/minute | <55 | >130 | Decrease >15 | Increase >15 |

Table 4: Criteria for Potentially Clinically Important ECG Values

| | | | | | |
|---------------|------|---|--|---|-----------------------------------|
| PR Interval | msec | - | ≥ 200 | - | - |
| QT Interval | msec | - | ≥ 440 | - | ≥ 30 and < 60 ≥ 60 |
| QTcF Interval | msec | - | ≥ 440 and < 480 ≥ 480 and < 500 ≥ 500 | - | ≥ 30 and < 60 ≥ 60 |

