18.3 Repeated or Unscheduled Assessments of Safety Parameters

If a subject has repeated assessments before the start of investigational product, then the results from the final assessment made prior to the start of investigational product will be used as baseline. If end-of-study assessments are repeated or unscheduled, the last post-baseline assessment while on investigational product will be used for generating descriptive statistics. However, all post-baseline assessments will be used for PCI value determination and all assessments will be presented in the data listings.

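### SAP 11.3 and 11.4 pair a by-visit denominator with an any-time numerator for PCI vital-sign and ECG values; followed literally, the percentages would be overstated as retention falls

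*SAP*

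**What the plan says.** SAP 11.3 gives the layout of the vital-sign PCI table: "The number and percentage of subjects with PCI post-baseline values will be tabulated by treatment group". No visit dimension is mentioned. For the observed-value criteria, percentages are taken "relative to the number of subjects with at least 1 post-baseline assessment available per parameter and visit". For the change-from-baseline criteria, the base is "the number of subjects with available baseline and at least 1 post-baseline assessment per parameter and visit". One numerator serves both: "The numerator is the total number of subjects with at least 1 PCI post-baseline vital sign value".

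SAP 11.4 uses the same two denominators for ECG values, with the parallel numerator: "The numerator is the total number of subjects with at least 1 PCI post-baseline ECG value".

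Both sections bring unscheduled visits into the PCI assessment. SAP 18.3 confirms this for repeated and unscheduled measurements: "all post-baseline assessments will be used for PCI value determination".

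The laboratory rule in SAP 11.2 has the same kind of numerator but a different base: "The percentages will be calculated relative to the number of subjects with at least 1 available post-baseline assessment per parameter". The visit does not appear there.

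**The concern.** The numerator covers the whole post-baseline period, while the denominator is tied to a visit. A child with a PCI reading at Visit 2 who leaves before Visit 5 is in the numerator but not in the Visit 5 denominator. The result is neither a by-visit rate nor an any-visit rate, and it grows as the number assessed at the visit falls.

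Blood pressure, pulse and ECG findings are part of the stated safety objective, and protocol section 1 names cardiovascular effects of amphetamine. These percentages will be read across placebo and four dose arms in children aged 4 to 5. If arms differ in retention, a literal calculation could make them look different for that reason alone. Two programmers could also produce different tables from the same text.

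**Working it through.** **Inputs.** SAP 2.2 and 2.5 give 195 randomized, 156 completers, 20% dropout and 5:5:5:5:6 allocation. The documents state no PCI rate and no arm-specific dropout, so those below are assumptions.

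**Plan's own figures.** 156/(1 − 0.20) = 195. Placebo: 195 × 6/26 = 45 randomized and 156 × 6/26 = 36 completers. Pooled 10, 20 and 30 mg: 195 × 15/26 = 112.5 and 156 × 15/26 = 90.

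**The three rules side by side.**
- Laboratory (11.2): any-time numerator, denominator per parameter. Matched.
- Vital signs (11.3): any-time numerator, denominator per parameter and visit. Not matched as worded.
- ECG (11.4): same as vital signs.

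**Formula.** Let p be the true any-visit proportion and d the share of subjects with no assessment at the visit. The literal rule gives p/(1 − d), an inflation factor of 1/(1 − d):
- d = 10%: 1/0.90 = 1.11
- d = 20%: 1/0.80 = 1.25
- d = 30%: 1/0.70 = 1.43

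**At planned dropout, assumed p = 20%.** Placebo: 9/45 = 20% becomes 9/36 = 25%. Pooled active: 22.5/112.5 = 20% becomes 22.5/90 = 25%.

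**Unequal dropout, assumed 10% placebo and 30% active, with p = 20% in both.** The table would show 0.20/0.90 = 22.2% against 0.20/0.70 = 28.6%.

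**Allowing for shorter follow-up in dropouts.** Assume a 10% chance per visit, independent visits, six visits for completers and three for dropouts. Then the any-visit chance is 1 − 0.9^6 = 0.469 for a completer and 1 − 0.9^3 = 0.271 for a dropout. In the placebo arm, 36 × 0.469 + 9 × 0.271 = 19.3 children have a PCI value. The matched any-visit rate is 19.3/45 = 43%; the literal rule at Visit 6 gives 19.3/36 = 54%. The numerator is smaller than if all 45 had six visits, but the ratio is still 45/36 = 1.25.

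**Consistent readings.** With both counts any-visit, the result is p and the factor is 1.00. With both counts restricted to the same visit, the factor is also 1.00.

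**The case against.** The strongest reply is that the text does not fix the inflated calculation. The table is by treatment group only, and elsewhere 11.3 and 11.4 say so when they want output by visit. Without visit rows there is no Visit 6 cell in which to divide by 36, and requiring at least one post-baseline assessment can be read as an any-visit base. Alternatively, the visit may be implied in the numerator. Either reading is harmless, and SAP section 1 leaves table specifications to a separate document. This stands as far as it goes: a reader might infer that the reported percentages will be too high, and the documents do not support that as a certainty. But each harmless reading needs words ignored or added. The any-visit reading drops the visit from the denominators. The by-visit reading adds a visit to the numerator and to the layout, and leaves unscheduled readings without a defined row.

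A reader might also infer that the numerator mixes parameters, since none is named. That does not hold: the 11.2 numerator omits the parameter too, and it is plainly implied in all three sections.

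The size is also open to challenge, and these limits stand:
- Protocol 7.1.2.3 has early terminators attend Visit 6/ET. If those data count at Visit 6, that denominator need not fall by the full 20%. They do not restore the Visit 4 and 5 denominators.
- Retention is higher at earlier visits, so the factor is smaller there.
- Higher dropout shortens follow-up and lowers the any-visit count, partly offsetting the arm distortion.
- Temperature has one scheduled post-baseline visit, so its mismatch is negligible.

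Finally, counts accompany the percentages, and all subjects with PCI values are listed, so the raw data remain visible.

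**Conclusion.** The concern holds in a limited form. As worded, numerator and denominator do not match in SAP 11.3 and 11.4, and SAP 11.2 shows the matched alternative. If programmed literally, percentages would be overstated by 1/(share assessed at the visit). At the planned 20% dropout that is at most about 1.25, reached only if all dropouts are missing at that visit. An arm with more dropout than planned would exceed this (1.43 at an assumed 30%), which is how unequal dropout would distort arm comparisons.

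Under either consistent reading the inflation is nil. The finding is therefore a rule that fails when followed as written, not proof that the published percentages will be wrong. No hypothesis test, alpha level or sample size is touched; only descriptive safety percentages are.

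**What to change.** In both 11.3 and 11.4:
- Delete the reference to visit from the two denominator sentences. The overall table is then subjects with at least one post-baseline PCI value for the given parameter and criterion, unscheduled visits included, over subjects with at least one post-baseline assessment of that parameter. For change criteria, also require a baseline value. This follows 11.2.
- Name the criterion in the numerator. Table 3's footnote treats a value as PCI if it meets either the observed-value or the change criterion, whereas the denominators are set separately for each.
- If a by-visit table is also wanted, restrict both counts to that parameter and that visit, and say how unscheduled readings are handled.

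The cost is a few sentences of SAP wording and the matching table shells. No new data are needed.

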11.5 Other Safety Variables**11.6 Children's Sleep Habits Questionnaire and Sleep Diary**

The CHSQ consists of 33 items for scoring and several extra items intended to provide administrators with other potentially useful information about respondents. The instrument evaluates the child's sleep based on behavior within 8 different subscales:

1. Bedtime resistance (sum of the responses for Goes to bed at same time, Falls asleep in own bed, Falls asleep in other's bed, Needs parent in room to sleep, Struggles at bedtime and Afraid of sleeping alone)
2. Sleep-onset delay (Falls asleep in 20 minutes item)
3. Sleep duration (sum of the responses for Sleeps too little, Sleeps the right amount and Sleeps same amount each day)
4. Sleep anxiety (sum of the responses for Needs parent in room to sleep, Afraid of sleeping in the dark, Afraid of sleeping alone and Trouble sleeping away)
5. Night wakings (sum of the responses for Moves to other's bed in night, Awakes once during night and Awakes more than once)
6. Parasomnias (sum of the responses for Wets the bed at night, Talks during sleep, Restless and moves a lot, Sleepwalks, Grinds teeth during sleep, Awakens screaming, sweating and Alarmed by scary dream)
7. Sleep-disordered breathing (sum of the responses for Snores loudly, Stops breathing and Snorts and gasps)
8. Daytime sleepiness (sum of the responses for Wakes by himself, Wakes up in negative mood, Others wake child, Hard time getting out of bed, Takes long time to be alert, Seems tired, Watching TV and Riding in car)

Each subscale and each individual item will be summarized using descriptive statistics (n, mean, SD, minimum, median, and maximum) at each visit (and Visit 8/ET) by treatment group. All CSHQ data will be listed for the Safety Analysis Set.

Sleep diary data will be summarized at each visit (and Visit 8/ET) for total daytime napping time, nighttime sleep time and time to fall asleep using descriptive statistics (n, mean, SD, minimum, median, and maximum) by treatment group. Sleep diary data are collected daily. The average daily value per visit and their change from baseline will be summarized by treatment group. Sleep diary data will also be listed for the Safety Analysis Set.

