### 1.2.2 Clinical Information

The pharmacological profile of lisdexamfetamine and the pharmacologically active metabolite *d*-amphetamine have been well-characterized in studies enrolling children, healthy adults, and adults with a history of stimulant abuse. These studies have demonstrated that oral administration of SPD489 resulted in a predictable *d*-amphetamine pharmacokinetic profile with low intrasubject and intersubject variability. The *d*-amphetamine  $AUC_{0-\infty}$  and  $C_{max}$  generally behaved in a linear, dose-proportional manner. The weight-normalized *d*-amphetamine  $AUC_{0-\infty}$  is similar for children and adults, with  $t_{max}$  and  $t_{1/2}$  consistent across age groups.

In the ADHD Clinical Development Program, the efficacy of SPD489 for the treatment of ADHD has been demonstrated for children, adolescents, and adults with ADHD. Substantial evidence of efficacy was provided in well-controlled studies, where SPD489 was shown to be effective compared to placebo. SPD489 was associated with a statistically significant, clinically meaningful improvement in ADHD symptoms, functional outcomes, and health-related quality of life compared to placebo, in studies that used a variety of study designs, a variety of validated assessments, and a variety of raters.

The well-characterized SPD489 safety profile was consistent with that of other stimulants used in the treatment of ADHD. When the safety results from the 15 completed Phase 2-4 clinical studies in the ADHD Clinical Development Program were examined, the majority of TEAEs were mild or moderate in severity, and no differences due to age or sex were noted. The most frequently reported adverse events (AEs) were those typically associated with stimulant therapy (including decreased appetite, insomnia, headache, dry mouth, irritability, upper abdominal pain, and weight decrease), or potentially attributable to intercurrent illnesses (eg, upper respiratory tract infection and nasopharyngitis). These TEAEs were generally non-serious and were considered by the investigator to be resolved during study participation.

Stimulant medications like SPD489 cause a modest increase in average blood pressure (about 2-4 mmHg) and average pulse (about 3-6 bpm). Individuals may have larger increases.

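### SAP 11.6 adds favourably and unfavourably worded CSHQ items in three subscales with no reversal, response coding or score direction, so the scores are incoherent if raw responses are summed as written

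*SAP*

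**What the plan says.** SAP 11.6 says that the CSHQ "consists of 33 items for scoring and several extra items" and that it "evaluates the child's sleep based on behavior within 8 different subscales". It then defines each subscale by naming its items:

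- Sleep duration is the "sum of the responses for Sleeps too little, Sleeps the right amount and Sleeps same amount each day".
- Bedtime resistance begins as the "sum of the responses for Goes to bed at same time, Falls asleep in own bed, Falls asleep in other's bed", followed by three more problem items.
- Daytime sleepiness begins as the "sum of the responses for Wakes by himself, Wakes up in negative mood, Others wake child", followed by five more problem items.
- The second subscale is a single item: "Sleep-onset delay (Falls asleep in 20 minutes item".
- The other four subscales (Sleep anxiety, Night wakings, Parasomnias, Sleep-disordered breathing) are sums of problem items only.

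Each subscale and each item is summarised descriptively by visit and treatment group, and all CSHQ data are listed. There is no test, cut-off or better/worse label. The same section summarises diary records of napping, night sleep and time to fall asleep.

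I found no response coding, direction or reversal rule in SAP 11.6, in the data-handling conventions of SAP section 18, or in Protocol 7.2.4.8 and 9.9. SAP 18.2 gives derivations for the ADHD-RS-IV, including its item scores, and for the CGI-I, but none for the CSHQ. Protocol Appendix 3 lists the CSHQ as a 2009 instrument with no version number, held in a separate master file.

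**The concern.** A subscale total can be read only if every item in it points the same way. In three of these sums the item names point in opposite directions. A child who starts to sleep too little, and so less often sleeps the right amount, moves two items of one total in opposite directions. Under Sleep-onset delay, a high frequency response means less delay.

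Sleep assessment is part of the safety objective (Protocol 2.2.2, SAP 3.2). Protocol 1.2.2 lists "decreased appetite, insomnia, headache, dry mouth, irritability" among the most frequently reported adverse events. By their names, Sleep-onset delay and Sleep duration lie close to insomnia, and they are the two subscales whose direction is most in doubt. At stake is whether the CSHQ subscale tables can be read correctly.

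**Working it through.** **Item count.** The SAP's lists contain 6 + 1 + 3 + 4 + 3 + 7 + 3 + 8 = 35 entries. Two items (needing a parent in the room, fear of sleeping alone) appear in both Bedtime resistance and Sleep anxiety, so there are 35 − 2 = 33 distinct items. This reproduces the stated 33.

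**Favourably worded items, read from the SAP's item names.** There are six: same bedtime, own bed, asleep in 20 minutes, right amount, same amount each day, wakes by himself. By subscale they are 2 of 6 in Bedtime resistance, 1 of 1 in Sleep-onset delay, 2 of 3 in Sleep duration and 1 of 8 in Daytime sleepiness.

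**Assumption.** The documents give no response scale. I take K frequency levels coded 1 to K and show K = 3, with 4 and 5 as a check.

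**Formula.** Take f favourable and p problem items, summed raw with high meaning more often:

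- best sleep = fK + p
- worst sleep = f + pK
- change from best to worst = (p − f)(K − 1)
- change if favourable items are reversed = (p + f)(K − 1)

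The fraction of the range kept is (p − f)/(p + f), whatever K is.

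| Subscale | f, p | Raw sum, best to worst (K = 3) | With reversal | Fraction kept |
|---|---|---|---|---|
| Sleep duration | 2, 1 | 7 to 5 | 3 to 9 | −1/3 |
| Sleep-onset delay | 1, 0 | 3 to 1 | 1 to 3 | −1 |
| Bedtime resistance | 2, 4 | 10 to 14 | 6 to 18 | 1/3 |
| Daytime sleepiness | 1, 7 | 10 to 22 | 8 to 24 | 3/4 |
| Parasomnias (no favourable items) | 0, 7 | 7 to 21 | 7 to 21 | 1 |

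Sleep duration goes from 9 to 6 for K = 4 and from 11 to 7 for K = 5. Sleep-onset delay goes from 4 to 1 and from 5 to 1.

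**Opposite coding (high = less often).** Every sign flips. Sleep duration rises from 5 to 7 and Sleep-onset delay from 1 to 3, but the other six subscales fall as sleep worsens (Parasomnias 21 to 7). Under one coding six subscales rise and two fall; under the other, two rise and six fall. In both, Sleep duration has a width of 2 instead of 6 (K = 3).

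**Changes short of the extremes.** For Sleep duration with K = 3, each item has 6 before/after pairs that are equal or worse. That gives 6³ = 216 combinations, less 3³ = 27 with no change, leaving 189 in which at least one item worsens and none improves.

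| Stored responses | Score falls | Unchanged | Score rises |
|---|---|---|---|
| Raw, high = more often | 116 | 34 | 39 |
| Raw, high = less often | 39 | 34 | 116 |
| Favourable items already reversed | 0 | 0 | 189 |

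**The case against.** The strongest reply is that the deciding input is missing. A reader might infer that the trial will report worse sleep as better sleep. The documents do not support that. The falls from 7 to 5 and from 3 to 1 need raw responses coded high for more often. With the opposite coding Sleep-onset delay rises as sleep worsens and Sleep duration mostly rises. If the database holds item-scored values, with the favourable items already turned round, the sums are correct. The SAP also attaches no better/worse label to any CSHQ score.

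Two other stronger readings fail. Mixed wording is not a fault of the CSHQ subscales in general: it affects three sums. Sleep-onset delay is not a mixed sum; its one item cannot cancel against anything, and only its direction is unstated.

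Nor would a sleep signal depend on these totals alone. The item tables show the sleep-amount and 20-minute items separately. The diary measures night sleep and time to fall asleep directly. Insomnia would also appear among treatment-emergent adverse events by preferred term (SAP 11.1).

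All of this stands, and it limits the consequence. It does not remove the defect, because the SAP states an operative rule, and following that rule on raw responses gives incoherent totals under either uniform frequency coding. If values are already item-scored, the item tables become the difficulty: a high mean for sleeping the right amount would then mean the opposite of its label.

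**Conclusion.** The point holds as a scoring rule that does not work on raw responses, with moderate severity. Three subscales add opposing items. On the assumed 1 to 3 scale, Bedtime resistance keeps one third of its range, Daytime sleepiness keeps three quarters, and the net best-to-worst change in Sleep duration is one third of its proper size, with a sign that depends on the coding. Sleep-onset delay keeps its full width but has no stated direction. The fractions do not depend on the number of response levels. The direction of the error does depend on the coding, which the documents do not give, and there is no error in the sums if stored values are already item-scored. The classification of six items as favourable rests on the SAP's short item names.

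The affected outputs are descriptive safety summaries. The primary, key secondary and dose-response analyses do not use the CSHQ.

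**What to change.** Before unblinding, confirm how CSHQ responses are stored, and then add to SAP 11.6:

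1. the response coding, and whether stored values are raw or already item-scored;
2. that the six favourably worded items (goes to bed at same time, falls asleep in own bed, falls asleep in 20 minutes, sleeps the right amount, sleeps same amount each day, wakes by himself) are reversed exactly once before summing;
3. that a higher score means more sleep problems in every subscale, Sleep-onset delay included;
4. a direction label on the item-level tables.

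The check of stored values has to come first. Reversing items that are already item-scored would create the error that the change is meant to prevent.

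The cost is a few sentences and one derivation line, with no new data. Section 11.6 needs editing in any case, since it refers to Visit 8/ET although the schedule of assessments ends at Visit 6/ET.
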